10.3.3 Evaluation of New Lesions

The finding of a new lesion should be unequivocal (i.e. not due to difference in scanning technique, imaging modality, or findings thought to represent something other than tumor (for example, some ‘new’ bone lesions may be simply healing or flare of pre-existing lesions)).

However, a lesion identified on a follow-up scan in an anatomical location that was not scanned at baseline is considered new and will indicate PD. If a new lesion is equivocal (because of small size etc.), follow-up evaluation will clarify if it truly represents new disease and if PD is confirmed, progression should be declared using the date of the initial scan on which the lesion was discovered.

10.3.4 Evaluation of Best Overall Response

The best overall response is the best response recorded from the start of the treatment until disease progression/recurrence (taking as reference for progressive disease the smallest measurements recorded since the treatment started). The subject's best response assignment will depend on the achievement of both measurement and confirmation criteria.

Table 2: For Subjects with Measurable Disease (i.e., Target Disease)

Target Lesions	Non-Target Lesions	New Lesions	Overall Response	Best Overall Response when Confirmation is Required*
CR	CR	No	CR	>4 wks Confirmation**
CR	Non-CR/Non-PD	No	PR	≥4 wks Confirmation**
CR	Not evaluated	No	PR	
PR	Non-CR/Non-PD/not evaluated	No	PR	
SD	Non-CR/Non-PD/not evaluated	No	SD	Documented at least once ≥4 wks from baseline**
PD	Any	Yes or No	PD	

Any	PD***	Yes or No	PD	no prior SD, PR or CR
Any	Any	Yes	PD	

* See RECIST 1.1 manuscript for further details on what is evidence of a new lesion.
 ** Only for non-randomized trials with response as primary endpoint.
 *** In exceptional circumstances, unequivocal progression in non-target lesions may be accepted as disease progression.
NOTE: Subjects with a global deterioration of health status requiring discontinuation of treatment without objective evidence of disease progression at that time should be reported as “*symptomatic deterioration.*” Every effort should be made to document the objective progression even after discontinuation of treatment.

Table 3. For Subjects with Non-Measurable Disease (i.e., Non-Target Disease)

Non-Target Lesions	New Lesions	Overall Response
CR	No	CR
Non-CR/non-PD	No	Non-CR/non-PD*
Not all evaluated	No	not evaluated
Unequivocal PD	Yes or No	PD
Any	Yes	PD
* ‘Non-CR/non-PD’ is preferred over ‘SD’ for non-target disease since SD is increasingly used as an endpoint for assessment of efficacy in some trials so to assign this category when no lesions can be measured is not advised		

10.4 Duration of Response

Duration of overall response: The duration of overall response is measured from the time measurement criteria are met for CR or PR (whichever is first recorded) until the first date that recurrent or progressive disease is objectively documented (taking as reference for progressive disease the smallest measurements recorded since the treatment started, or death due to any cause. Subjects without events reported are censored at the last disease evaluation).

Duration of overall CR: The duration of overall CR is measured from the time measurement criteria are first met for CR until the first date that progressive disease is objectively documented, or death due to any cause. Subjects without events reported are censored at the last disease evaluation.

Duration of SD: SD is measured from the start of the treatment until the criteria for progression are met, taking as reference the smallest measurements recorded since the treatment started, including the baseline measurements.

10.5 Immune-Related Response Criteria (irRC)

The sum of the products of the two largest perpendicular diameters of lesions (SPD; 5 lesions per organ, up to 10 visceral lesions) at tumor assessment using the immune related response criteria (irRC) for progressive disease incorporates the contribution of new measurable lesions (up to 5 new lesions per organ: 10 new visceral lesions).³⁴ Each net Percentage

Change in Tumor Burden per assessment using irRC criteria accounts for the size and growth kinetics of both old and new lesions as they appear.

10.5.1 Definition of Index Lesions Response Using irRC

irComplete Response (irCR): Complete disappearance of all target lesions in two consecutive observations not less than 4 weeks apart. This category encompasses exactly the same subjects as “CR” by the mWHO criteria.

- irPartial Response (irPR): Decrease, relative to baseline, of 50% or greater in the sum of the products of the two largest perpendicular diameters of all target and all new measurable lesions in two consecutive observations not less than 4 weeks apart. (i.e., Percentage Change in Tumor Burden). Note: the appearance of new measurable lesions is factored into the overall tumor burden, but does not automatically qualify as progressive disease until the SPD increases by > 25% when compared to SPD at nadir.
- irStable Disease (irSD): Does not meet criteria for irCR or irPR, in the absence of progressive disease.
- irProgressive Disease (irPD): At least 25% increase in the percentage change in tumor burden (i.e., taking SPD of all target lesions and any new lesions) when compared to SPD at nadir, in two consecutive observations at least 4 weeks apart, in the absence of rapid clinical deterioration.

10.5.2 Definition of Non-Index Lesions Response Using irRC

- irComplete Response (irCR): Complete disappearance of all non-index lesions. This category encompasses exactly the same subjects as “CR” by the mWHO criteria.
- irPartial Response (irPR): Non-index lesion(s) are not considered in the definition of PR; this term does not apply.
- irStable Disease (irSD): Does not meet the criteria for irCR or irPD.
- irProgressive Disease (irPD): Increases in number or size of non-index lesion(s) does not constitute progressive disease unless/until the Percentage Change in Tumor Burden increases by 25% (i.e., the SPD at nadir of the target lesions increases by the required amount).

10.5.3 Impact of New Lesions on irRC

New lesions in and by themselves do not qualify as progressive disease. However, their contribution to total tumor burden is included in the SPD which in turn feeds into the irRC criteria for tumor response. Therefore, new non-measurable lesions will not discontinue any subject from the study.

10.5.4 Definition of Overall Response Using irRC

Overall response using irRC will be based on these criteria:

- Immune-Related Complete Response (irCR): Complete disappearance of all tumor lesions (index and non-index together with no new measurable/unmeasurable lesions) for at least 4 weeks from the date of documentation of complete response.
- Immune-Related Partial Response (irPR): The sum of the products of the two largest perpendicular diameters of all index lesions is measured and captured as the SPD

baseline. At each subsequent tumor assessment, the SPD of the two largest perpendicular diameters of all index lesions and of new measurable lesions are added together to provide the Immune Response Sum of Product Diameters (irSPD). A decrease, relative to baseline of the irSPD compared to the previous SPD baseline, of 50% or greater is considered an immune Partial Response (irPR).

Immune-Related Stable Disease (irSD): irSD is defined as the failure to meet criteria for immune complete response or immune partial response, in the absence of progressive disease.

- Immune-Related Progressive Disease (irPD): It is recommended to confirm PD by serial imaging. Any of the following will constitute progressive disease:
 - At least 25% increase in the SPD of all target lesions over nadir SPD calculated for the index lesions, in two consecutive observations at least 4 wk apart, if clinically permissible*.
 - At least a 25% increase in the SPD of all index lesions and new measurable lesions (irSPD) over the nadir SPD calculated for the target lesions, in two consecutive observations at least 4 wk apart, if clinically permissible*.

Table 4. Immune-Related Response Criteria Definitions

Target Lesion Definition	Non-Target Lesion Definition	New Measurable Lesions	New Unmeasurable Lesions	Percent Change in Tumor Burden (including measurable new lesions when present)	Overall irRC Response
Complete Response	Complete Response	No	No	-100%	irCR*
Partial Response	Any	Any	Any	≥-50%	irPR*
				<-50% to <+25%	irSD*
				>+25%	irPD*
Stable Disease	Any	Any	Any	<-50% to <+25%	irSD*
				>+25%	irPD*
Progressive Disease	Any	Any	Any	≥+25%	irPD*

* In two consecutive observations at least 4 weeks apart, if clinically permissible*

10.5.5 Immune-Related Best Overall Response Using irRC (irBOR)

irBOR is the best confirmed irRC overall response over the study as a whole, recorded between the date of first dose until the last tumor assessment before subsequent therapy (except for local palliative radiotherapy for painful bone lesions) for the individual subject in the study. For the assessment of irBOR, all available assessments per subject are considered. irCR or irPR determinations included in the irBOR assessment must be confirmed by a second (confirmatory) evaluation meeting the criteria for response and performed no less than

4 weeks after the criteria for response are first met.

10.6 Response Review

Tumors will be assessed for response and progression by RECIST version 1.1 by central radiology review.

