2.7 Study Design

This is a phase II study investigating a response-based approach to therapy with nivolumab and ipilimumab in subjects with advanced renal cell carcinoma (RCC). All subjects will initiate therapy with nivolumab. After 8 weeks (± 7 days), subjects will undergo the first response assessment, as well as additional assessments for the response confirmations if applicable, then be assigned to the study arms A and B. Confirmation scans for patients with CR/PR/SD will occur following an additional 8 weeks (± 7 days). For patients with PD, initial confirmation scans will be obtained at 4 weeks (± 7 days) at the discretion of the treating investigator if the patient is stable to wait for confirmatory imaging. Arm allocation will occur within the first 6 months of the study. For subjects to be allocated to Arm A, they need to have a confirmed CR/PR on two serial and consecutive imaging assessments within the first 6 months of the study while on nivolumab treatment alone. All other subjects who are not able to demonstrate a persistent confirmed CR/PR within the first 6 months of the study, will be allocated to Arm B.

Single Cell Sequencing Cohort: An additional subset of patients (n=25) will be enrolled to the study at DFCI and selected sites with capability for single cell molecular transcriptomic assessment. These patients will receive the same treatment as detailed above and will be allocated in Arm A and B as detailed above. All patients will undergo a mandatory baseline biopsy. Biopsy schedule by treatment arm is detailed below:

Arm A:

Mandatory biopsy at baseline

Optional biopsy at time of response following discontinuation of nivolumab

Mandatory biopsy at final treatment discontinuation/off study

Arm B:

Mandatory biopsy at baseline

Mandatory biopsy at final treatment discontinuation/off study

Arm A (persistent PR/CR) includes the following patient scenarios:

- Subjects who experience a partial response (PR) or complete response (CR) at 8 weeks (initial response assessment) from initiation of primary nivolumab therapy and who maintain a persistent PR or CR at the subsequent imaging assessment in 8 weeks (± 7 days) (i.e., ~16 weeks from initiation of nivolumab);

OR

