- Subjects who experience stable disease (SD) at the initial response assessment at 8 weeks from initiation of primary nivolumab therapy, with the subsequent scan in 8 weeks (± 7 days) documenting CR/PR which is maintained at the next imaging assessment in 8 weeks (± 7 days) (i.e., ~24 weeks from initiation of nivolumab).

Patients who have SD on initial assessment followed by CR/PR on first confirmatory assessment which does not persist on the second confirmatory imaging assessment will be allocated to Arm B as CR/PR was not persistent and confirmed on consecutive imaging assessments.

Subjects with confirmed PR/CR (arm A) will discontinue nivolumab and be followed with serial imaging assessments every 8 weeks. If progressive disease (PD) develops, therapy with nivolumab will be resumed and will not be discontinued if a subsequent PR or CR were to occur. Subjects who experience subsequent PD following re-initiation of nivolumab, will be treated with nivolumab + ipilimumab every 3 weeks x 2 doses and will continue nivolumab. All patients will continue on treatment with nivolumab alone every 4 weeks which will begin 5 weeks \pm 3 days after the last dose of nivolumab + ipilimumab. For subjects who experience a PD on nivolumab and ipilimumab, treatment will be discontinued.

If by 24 weeks, subjects have not demonstrated a persistent CR/PR confirmed on at least two serial scan assessments, then subjects will be allocated to Arm B at the 24 week time point.

Arm B (persistent PD/SD) includes the following patient scenarios:

- Subjects who experience PD at 8 weeks (initial response assessment) on primary nivolumab therapy which is then confirmed by a second scan within 4 weeks (\pm 7 days). The confirmatory scan is not required if the site investigator determines that this is clinically detrimental;
- Subjects who initially experience SD at 8 weeks (initial response assessment), which is confirmed with a second scan showing SD in 8 weeks (\pm 7 days)
- Subjects who have received at least 3 doses of nivolumab and may have signs and/or symptoms concerning for early clinical progression with radiographic evidence of PD before 8 weeks
- Subjects who do not meet the criteria for allocation into Arm A given lack of persistent CR/PR confirmation on serial and consecutive imaging within the first 6 months of the study will be allocated to Arm B by the 6-month time point.

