- 4: TSH and free T4 will be done at screening and every 2 cycles (8 weeks ± 7 days).
- 5: For women of childbearing potential (WOCBP): urine or serum βhCG. If a urine test is done and it is positive or cannot be confirmed as negative, a serum pregnancy test will be required. WOCBP should be counseled regarding the importance of contraception from the time of screening until 180 days after last dose of study drug(s). If a subject communicates that pregnancy is possible, a serum βhCG should be performed per site investigator's discretion.
- 6: Hepatitis B virus (HBV) serology (HBsAg, antibodies against HBsAg, antibodies against hepatitis B core antigen), and HCV serology (anti-HCV) will be performed. HBV DNA test is required for subjects who have known positive serology for anti HBc. HCV RNA test is required for subjects who have known positive serology for anti HCV.
- 7: Radiology Imaging at screening to include: Diagnostic CT chest and CT or MRI of the abdomen and pelvis and MRI of the brain. If a subject is not able to obtain an MRI, CT imaging with contrast is acceptable. If a subject is not able to receive contrast, CT head without contrast is acceptable. Radiology Imaging during Primary Treatment: Initial scans will be done after 2 cycles (8 weeks +/- 7 days) of nivolumab. Subjects with PR/CR/SD will have confirmatory scans 8 weeks later (+/- 7 days). Confirmatory scans for subjects with PD are not mandatory but may be attained 4 weeks later if clinically feasible (+/- 7 days). Subjects who have two serial consecutive imaging assessments (8 weeks +/- 7 days apart) which demonstrate CR/PR within the first 6 months of study will be allocated to Arm A. All other subjects who do not meet this criteria will enter Arm B by the 6 month time point. Subjects have who signs and/or symptoms concerning for early clinical progression can undergo imaging before 8 weeks (+/- 7 days). In this scenario, if there is evidence of radiographic progression, subjects may be allocated to Arm B immediately, assuming they have received at least 3 doses of nivolumab. For Single Cell Sequencing Cohort MRI or CT of the Brain will not be collected at screening.
- 8: Primary Treatment: Nivolumab will be administered on Day 1 (+/- 3 days) of each 28-day cycle for 2 cycles. After 2 cycles, disease assessment will occur. Nivolumab alone will continue until disease status documented with confirmatory scans (See Footnote 7) or site investigator

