9.4 Radiology Imaging Studies

Images of all radiologic assessments at baseline, on study, and at treatment discontinuation with corresponding imaging reports for non-DFCI patients need to be placed on a CD and sent to the DFCI for eventual central review of exploratory imaging response assessment by irRC. Images and reports should be sent on all patients once they discontinue study treatment. Please ensure that patient data is de-identified and patient study ID is referenced on all materials as detailed in the lab manual. Reference the Laboratory Manual for additional information.

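### The plan names a central RECIST reader but gives that reader no images in time for allocation at non-DFCI sites, so a change of reader could count as an Arm B conversion

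*Combined protocol and SAP*

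**What the plan says.** Section 10.6 assigns the reading: "Tumors will be assessed for response and progression by RECIST version 1.1 by central radiology review". Section 9.4 is the only place that describes how images reach a central reader. It says that scans and "imaging reports for non-DFCI patients need to be placed on a CD and sent to the DFCI for eventual central review", describes the purpose as "eventual central review of exploratory imaging response assessment by irRC", and sets the time: "Images and reports should be sent on all patients once they discontinue study treatment".

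Allocation comes much earlier. Section 2.7 says "Arm allocation will occur within the first 6 months of the study" and "For subjects to be allocated to Arm A, they need to have a confirmed CR/PR on two serial and consecutive imaging assessments", without saying who reads them. The site has a stated role only for progression. In 2.7, after PD, "The confirmatory scan is not required if the site investigator determines that this is clinically detrimental". In the primary-treatment calendar of Section 8, footnote 8 reads "Nivolumab alone will continue until disease status documented with confirmatory scans (See Footnote 7) or site investigator", and the sentence goes on to the site's own confirmation of PD. Section 6.7 also speaks of progression as assessed by the site.

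Sections 13.2.1 and 13.7.1 define the primary endpoints by RECIST 1.1 and name no reader. Section 10.3.1 measures PR against the baseline sum, and no new baseline is set when ipilimumab starts. Under 2.7, Arm B subjects with CR, PR or SD after ipilimumab stay on nivolumab.

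**The concern.** Arm B is defined by not having responded, and its endpoint is having responded. If one reader decides the first and another the second, some of the apparent change is only a change of reader. A subject read as SD at the site but already PR centrally at allocation goes to Arm B. If still PR on a later central read, that subject counts as a conversion although the tumour has not changed. The reverse case, PR at the site and SD centrally, goes to Arm A with no central response to continue.

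The two errors do not offset each other, because each arm has its own endpoint and decision rule. Arm B is sensitive because 6 responders among 57 are enough to declare the regimen worthy of further study.

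**Working it through.** **Step 1. Which reads can exist when.** At allocation a subject is on nivolumab, within six months of starting. For a non-DFCI patient the described transfer has not yet happened, so no central read from it exists and allocation must use a local read. The same holds for any Arm B stage-1 decision while those subjects are on treatment. Because Arm B responders continue nivolumab, their images may also be missing at the primary analysis, which 13.3 expects at about 2 years. DFCI images need no shipment, and the plan does not state who reads them.

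**Step 2. Reproduce the Arm B design (13.3).** Inputs: 20 subjects in stage 1, stop at 1 or fewer responders, 57 in total, success at 6 or more, null rate 5%, alternative 20%.

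P(active | p) = Σ over x = 2 to 20 of P(Bin(20, p) = x) × P(Bin(37, p) ≥ 6 − x)

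- p = 0.05: 0.0476 (plan: 4.7%); early stopping 0.736 (plan: 73%)
- p = 0.20: 0.921 (plan: 92%)

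The design reproduces. The printed 4.7% and 73% are truncated, which is not an error of design.

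**Step 3. Add a fixed number k of discordant subjects.** The documents give no site-versus-central discordance rate, so k is assumed. Each of the k subjects is counted as a conversion with certainty, and all others convert at 5%. The number j falling in stage 1 has probability C(20, j) × C(37, k − j) / C(57, k). Stage 1 then yields j + Bin(20 − j, 0.05), and stage 2 yields (k − j) + Bin(37 − k + j, 0.05).

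For k = 1: (20/57) × 0.1339 + (37/57) × 0.0967 = 0.0470 + 0.0628 = 0.110.

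| k of 57 | Early stopping | P(active) at true 5% |
|---|---|---|
| 0 | 0.736 | 0.048 |
| 1 (1.8%) | 0.610 | 0.110 |
| 2 (3.5%) | 0.482 | 0.223 |
| 3 (5.3%) | 0.367 | 0.393 |

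**Step 4. The same as a rate c.** Apparent conversion rate p = 1 − 0.95 × (1 − c), put into the formula of step 2. The last column assumes that only half of the discordant subjects are still PR centrally when the endpoint is read, so c is halved.

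| c | p | P(active) | P(active) if half remain PR |
|---|---|---|---|
| 2% | 0.0690 | 0.150 | 0.091 |
| 3% | 0.0785 | 0.222 | 0.119 |
| 5% | 0.0975 | 0.386 | 0.185 |

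**Step 5. Arm A.** The rule in 13.3 (5 or more of 23) has 7.3% probability of success at a true 10% and 94.5% at 35%. If 2 of 23 (assumed) could not count as continued responders, power at 35% is P(Bin(21, 0.35) ≥ 5) = 90.8%. The loss is modest.

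**The case against.** The strongest reply is that this is a gap in wording and not a demonstrated bias. Section 9.4 concerns an exploratory irRC review and need not describe the logistics of the RECIST review in 10.6. If central RECIST reads were made in real time, or if central review were exploratory only and the site read governed throughout, one reader would apply and the inflation would be zero. That stands: the effect needs a local read at allocation, a central read for the endpoint and no reconciliation between them. But 10.6 as written gives response to the central reader, and the plan describes no earlier route for non-DFCI images.

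Three stronger readings are tempting and are not supported:

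- A reader might infer that all arms are allocated on site reads. Timing forces this only at non-DFCI sites. For DFCI patients the reader is unstated, and the site's stated role concerns PD, not SD or PR.
- A reader might infer that a subject who is SD centrally on entering Arm A can never count. Section 13.2.1 looks at status at 1 year, and a later central PR is possible. Whether it would count as remaining in response is undefined.
- A reader might take 11% to 39% as the expected error rate. It is an upper figure for each assumed count. A discordant subject must still be PR at or after the first post-ipilimumab scan at 12 weeks, and Table 2 in 10.3.4 indicates confirmation of response. Central PR alongside site PD is also less plausible than alongside site SD. With the 40:35 SD to PD split in 13.3, about 57 × 40/75 = 30 subjects are SD, so 5% of Arm B (2.85 subjects) means about 9% of the SD group.

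It is also fair to say that one reader does not cure everything. A subject just short of PR at allocation can drift across the 30% threshold under the same reader, because the reference stays the pre-nivolumab baseline. That is a separate matter.

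**Conclusion.** The concern holds in a conditional form. Sections 9.4 and 10.6 do not fit together, and no section names the reader for allocation of SD, PR or CR, for the interim decisions or for the primary endpoint. Followed together, they let reader disagreement at non-DFCI sites enter the Arm B numerator, and nothing in the plan prevents it.

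The size is illustrative because the discordance rate is assumed. At a true 5% conversion rate the false-positive probability rises from 4.8% to 11%, 22% or 39% for 1, 2 or 3 subjects of 57. At assumed rates of 2%, 3% or 5% it is 15%, 22% or 39%, or about 9%, 12% or 19% if only half remain PR. With one reader throughout, the design keeps its 4.8% and 92%. The documents do not establish that the bias will occur.

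**What to change.** 1. Reconcile 9.4 with 10.6, and state in 10.6 and 13.2.1 who reads the scans for allocation, for the interim looks and for the primary endpoint. Entry status and endpoint should use the same reader. Which reader is primary is the sponsor's choice: site reads are available in time but are unblinded, while central reads keep 10.6 but need earlier images.
2. Wherever the central read is used, as primary or sensitivity analysis, count an Arm B conversion only if the central read at allocation was SD or PD, and Arm A persistence only if it was CR or PR.
3. In 9.4, require non-DFCI baseline, allocation and follow-up images before the primary analysis rather than only after discontinuation. Otherwise the images of Arm B responders still on nivolumab may be missing.

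The cost is wording in three sections, earlier image transfer from non-DFCI sites, and slightly fewer countable subjects in the central-read analysis. Central RECIST reads are already called for in 10.6.
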